9 GENERAL STUDY PROCEDURES

Screening

Research Coordinators (RCs) will work in conjunction with the site investigators to identify patients who meet eligibility criteria at their respective site. Candidates will be initially screened either in person or by phone. For eligible candidates who express interest in participating, a Screening and Enrollment Visit will be scheduled (Visit 1). These candidates may be provided a copy of the informed consent along with supplemental materials that illustrate the device to review prior to Visit 1.

Enrollment and Screen Failures

At Visit 1, subject eligibility will be reviewed. Subjects who are still eligible and have provided written informed consent by signing the Informed Consent Form (ICF) will be considered for enrollment. Subjects will be provided a copy of the signed ICF.

Subjects will be considered enrolled in the study when they have completed training, are successfully fitted with a WCD System, the Monitor is connected to the Garment and the System is powered ON. Subjects who are consented but not enrolled per this definition will be classified as screen failures.

Subject Identification Numbers

Each enrolled subject will be assigned a unique subject identification (SID) number. The first three characters of the SID will reflect the study site number (e.g. S01, S02, ..., S10). The Sponsor will inform each site of its designated site number before the site is opened for enrollment. The last two digits will be assigned based on the enrollment sequence (e.g. the first subject enrolled at each site will be assigned 01) and will be separated from the site designation by a hyphen e.g. S01-05 is subject 05 enrolled at site 01. This number will be used on the Case Report Form (CRF) and on the CareStation website data uploads. The Sponsor will not collect Protected Health Information that would allow specific subject identification (e.g. date of birth, name, initials, medical record number) on the CRF or in the WCD system data.

Unscheduled Visits

Unscheduled visits may be necessary due to AEs or other reasons. The Investigator may examine a subject as often as is medically necessary while the subject is enrolled in the study. Assessments performed at unscheduled visits are at the discretion of the Investigator and will be documented in the CRFs.

Phone Calls

Research Coordinators will conduct weekly phone interviews with the subjects during the participation period to address subject questions, review potential adverse events, and review usage. Unscheduled Study-related phone calls to or from the subjects may also occur.

Subject Withdrawals

Subjects may be withdrawn from the study for any reason including the following:

- Adverse Events (The Medical Monitor will consult with the Site Investigator)
- Investigator/Sponsor decision to withdraw subject from study
- Subject withdrawal of consent

Subjects who require temporary hospitalization (less than 72 hours) for non-study related complications are not required to withdraw from the study but may interrupt use of the WCD during this period at the Investigator's discretion.

When a subject is withdrawn from the study, the reason(s) for withdrawal will be recorded in the case report form (CRF). For any subject who withdraws due to an AE, the reason for withdrawal must be recorded as an AE. Whenever possible, all subjects who are being withdrawn from the study prematurely will undergo assessments listed for the Early Withdrawal visit. Every effort will be made to perform the same procedures at an Early Withdrawal Visit as the Study Exit Visit.

A subject who fails to return for any scheduled visit will be contacted by the site personnel with every effort made to have the subject comply with the protocol. After enrollment, if a subject cannot be contacted with a minimum of 3 telephone calls or emails over a period of 2 weeks (+/- 4 days) including a certified letter, the reason for withdrawal will be recorded as "lost to follow-up". If no response is received, the study withdrawal date will be documented as the date the certified letter was mailed. Every effort will be made to retrieve all study system components regardless of the reason for end of study participation.

In the event of a subject death during the study, the date of death (as listed on the death certificate) will be used as the date of study withdrawal.

AEs deemed by the investigator to be at least possibly related to the use of the ASSURE WCD system persisting at the time of the subject's study exit will be followed by the investigator until the events are resolved, the subject is lost to follow-up or the adverse events are otherwise explained. If further evaluations are required, the investigator will ensure that relevant additional information is documented in the CRF.

Medical Monitor

The Medical Monitor (an independent physician not participating as a clinical investigator in the clinical study) will review and assess in conjunction with the Sponsor all AEs considered by the investigator to be at least possibly related to the use of the ASSURE WCD System to determine if they are reportable to the FDA as Unanticipated Adverse Device Effects (UADEs) per the definition in Section 11. The Medical Monitor will also review all Serious Adverse Events considered by the investigator to be at least possibly related to the use of the ASSURE WCD System to the ASSURE WCD System to verify relatedness and the Serious classification.

Endpoint Review Committee

An independent panel of board-certified electrophysiologists (physicians not participating as clinical investigators in the clinical study) will review all episodes recorded by the ASSURE WCD and/or the subject's ICD in accordance with the *Endpoint Review Committee (ERC) Charter for ASSURE WCD Clinical Evaluation - Detection and Safety Study (ACE-DETECT)* (3334131). These annotations will then be used in the statistical analysis to classify the episodes to calculate the study outcome measures.

Replacements

Subjects who are withdrawn from the study will not be replaced.

Sponsor or Regulatory Agency Termination of the Study

Although the Sponsor intends to complete the study, the right is reserved to discontinue the study at any time for clinical or administrative reasons, or if required by the local regulatory authority.

End of Study

The end of study will be defined as the date of the last visit of the last subject. A summary of the End of Study report will be sent to relevant regulatory authorities and Institutional Review Boards (IRBs) within 6 months of the end of the study.

10 STUDY VISIT PROCEDURES

The Schedule of Events is presented in Appendix A. A detailed description of assessments performed at each study visit is presented below.

Visit 1 (Day 0): Screening and Enrollment

The ASSURE System Training Manual provides detailed instructions for WCD fitting, programming, and System power ON. The following process will be followed at Visit 1.

- Review eligibility criteria
- Explain the purpose and conduct of the study visits to the subject, answer the subject's questions, and obtain written informed consent. This consent process can be performed in advance of Visit 1 at the discretion of the site Investigator.
- Provide the subject with a copy of the signed informed consent
- Obtain demographic data
- Collect ICD Baseline Documentation:
 - Perform a full interrogation of the ICD on the Day of enrollment prior to WCD garment fitting.
 - Synchronize the ICD internal clock to the current time and time zone.
 - If current programmed parameters do not include detection as low as 150 bpm, the Sponsor requests that a monitoring zone at 150 bpm be programmed at the approval of the subject's physician. (ICD data will be used to identify WCD Missed Events (False Negative Detections)).
 - Print the ICD report as part of the source documentation. The report shall include the programmed parameters and arrhythmic episode history.
- Obtain abbreviated limited medical history as specified in the Case Report Form (CRF).
- Perform Wearability Assessment as specified in the CRF. If there is any question regarding skin condition e.g. eczema, the site investigator shall use medical judgement to determine if it disqualifies the subject from participating.
- Obtain urine pregnancy test for women of childbearing potential. If positive, subject is ineligible to participate.
- Perform subject training, including overview of study procedures, hands-on assembly and disassembly of the garment and cable assembly, use and care of the

WCD, and review of manuals. Sponsor representative(s) may be available to assist.

- Have the subject complete the BORG Comfort Scale before they are fit with the Garment. This provides a baseline comfort level to which the follow up BORG Scale scores (obtained at Visit 2 after the subject has worn the WCD) can be compared.
- Fit Garment to subject in accordance with the sizing chart and instructions provided in the System Training Manual. *Subjects with an under bust chest circumference greater than 52 inches or less than 28 inches are not eligible to be enrolled.*
- Photograph Garment fit (torso only, not subject's head) from both lateral views, the anterior view and the posterior view.
- Set up the WCD including subject ID entry, and synchronization of the WCD internal clock to the current time and time zone. VT/VF detection parameters will remain at default settings. (Refer to the System Training Manual).
- Register the study subject on the CareStation remote monitoring website (Add New Patient) using their study subject ID number.
- Verify Garment fit per System Training Manual using the tablet. Save tablet screen images of the Patient Management, Device Status and WCD Settings screens including the ECG signals.
- Schedule subject to return for follow up (Visit 2)
- Notify the subject that they will receive phone calls on Days 7 +/- 2, 14 +/-2, 21+/- 2, and 28 +/- 2 during which they can ask questions, and during which they will be asked about usage (how long they have been wearing the system), and if they experienced any discomfort or injury. Schedule these weekly phone calls with the subject.

Weekly Phone Calls to Study Subject

On each of Day 7 +/- 2, Day 14 +/- 2, Day 21 +/- 2, and Day 28 +/- 2 the site RC will call the study subject. In preparation for the call, the RC will review daily usage using the CareStation website and will record the usage data in the CRF.

• Record subject questions and responses in the CRF, noting any questions that require additional follow up and when the subject was called again with the answer(s).

Kestra Medical Technologies, Inc. Protocol 3324582_B

- Record subject's explanation for any usage less than 22 hours per day³ since the previous call.
- Ask the subject if they have experienced any discomfort or injury during the previous week. If yes, and the investigator determines that the symptoms are at least possibly related to use of the system, record as an AE in the CRF and gather supporting documentation as appropriate, e.g. description, photograph.

Visit 2: Study Exit Visit

At Visit 2 the following will be performed:

- Photograph garment fit (torso only) from both lateral views, the anterior view and the posterior view.
- Remove the Garment.
- Record WCD System Return (all components).
- Perform Wearability Assessment after system removal as indicated in the CRF.
- Ask the subject if they have experienced any discomfort or injury since the last phone call. If yes, and the investigator determines that the symptoms are at least possibly related to use of the device, record as an AE in the CRF.
- Have the subject complete the follow up BORG Comfort Scale.
- Have the subject complete the Usability Survey.
- Record subject explanation for usage less than 22 hours per day since the last weekly phone call.
- Obtain ICD summary report via the ICD remote management system or direct interrogation (model number, current programmed parameters, episode detail and any stored electrograms that are available from all new episodes recorded since Visit 1). De-identify and label with subject ID.
- Release the subject from the Visit.

³ Average WCD wear time reported in WEARIT-II Registry Trial (Kutyifa V)

Following the Study Visit:

- Follow up requirements for subjects with ongoing AEs are specified in Section 11.
- If follow-up is needed after the Study Exit visit, it should occur as an unscheduled visit at the Investigator's discretion.

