11 STUDY ASSESSMENTS

This section describes the study assessments. For timing of study assessments, see the Schedule of Events (Appendix A).

Demographic Data

Demographic data, such as age, sex, race, and ethnicity will be collected on the CRF

Abbreviated Medical History

An abbreviated medical history as specified in the CRF, including but not limited to cardiac diagnosis and skin allergies will be obtained for each subject at screening and updated any time the Investigator learns of information that might affect the subject's eligibility to continue participation in the study or to identify AEs.

ICD Interrogation and Report Generation

ICD Interrogation at Visit 1 (collect Baseline ICD Documentation via direct interrogation) and at Visit 2 (Obtain ICD summary report via the ICD remote management system or direct interrogation) must be done by qualified site personnel.

BORG Comfort Scale

Subjects will be asked by the research coordinator at baseline and again at the follow up visit to locate and grade the severity of any discomfort they experience on their upper body. This will be recorded on a BORG comfort scale/map as specified in CRFs.

Wearability Assessment

A Wearability Assessment (as specified in the CRF), including a review of skin abnormalities on the upper body and/or musculoskeletal conditions, and measurement of height and weight, will be performed by study personnel. Abnormal findings at Visit 1 will be used to reassess eligibility. If the subject is enrolled, then the findings will be recorded in the CRFs as baseline conditions. The Wearability Assessment will also be performed at Visit 2 after the System has been removed. Height will not be measured or recorded at Visit 2. Abnormal findings that were not present at baseline or have worsened from baseline and are determined by the investigator to be at least possibly related to use of the WCD will be recorded in the CRFs as AEs.

Concomitant Medical Devices and Equipment

Use of allowed concomitant medical devices and durable medical equipment will be recorded in the CRFs (e.g. CPAP, walker, wheelchair).

Clinical Laboratory Tests

Pregnancy testing by urinalysis will be performed for women of child bearing potential to verify eligibility prior to enrollment. Test sticks will be provided by the Sponsor.

Evaluation of Adverse Events

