Adverse events (AEs) as defined below will be monitored continuously during the study from the time the subject is considered enrolled through resolution. Subjects will be instructed to report all AEs during the study, and study personnel will interview the subjects regarding new AEs during each weekly phone call follow up. AEs may be reported by the subject, discovered by Investigator questioning, or detected through physical examination or other means at the study exit visit.

Device Usability Survey

A device Usability Survey will be administered at Visit 2.

Definitions

For the purposes of this study, an **AE** is defined as any untoward medical occurrence in a subject during the study that in the opinion of the investigator is at least possibly-related to use of the ASSURE WCD System.

A serious adverse event (SAE) is defined as any adverse event that:

- Leads to death
- Leads to serious deterioration in the health of a subject that:
 - Results in a life-threatening illness or injury, or
 - Results in a permanent impairment of a body structure or a body function, or
 - Requires in inpatient or prolonged hospitalization \geq 24 hours, or
 - Results in medical or surgical intervention to prevent life-threatening illness or injury or permanent impairment to a body structure or function, or
 - Leads to fetal distress, fetal death or a congenital anomaly or birth defect.

Adverse Device Effect (ADE) is an adverse event related to the use of an investigational medical device.

Anticipated Adverse Device Effects (AADE) are those events related to the use of the device that are reasonably expected to occur as a result of the subject's participation in

the study. The following are AADEs based on results from the series of previous feasibility studies listed in Section 6 and the system engineering hazard analysis:

- Mild to moderate skin irritation
- Muscle Strain
- Emotional discomfort e.g. anxiety, uncomfortable or claustrophobic feelings
- Fall Injury
- Bruising
- Pinched Fingers
- Shoulder discomfort
- Skin Infection (bacterial or yeast)
- ICD System Infection

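### Minor safety gap: the study-requested ICD monitoring zone is listed ahead of three checks that can still exclude a subject, and events due only to the ICD work are not recorded as adverse events

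*Protocol*

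**What the plan says.** Protocol 10, Visit 1, sets out the visit as a list of steps to be followed. It opens with an eligibility review and consent. The ICD step comes soon after: "Perform a full interrogation of the ICD on the Day of enrollment prior to WCD garment fitting", synchronise the ICD clock, and, where detection does not reach down to 150 bpm, "the Sponsor requests that a monitoring zone at 150 bpm be programmed at the approval of the subject's physician". The reason given is that ICD data will be used to identify WCD Missed Events. The ICD report, including its programmed parameters, is then printed.

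Three checks that bear on eligibility are listed after this step:

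- The Wearability Assessment. Protocol 11 adds: "Abnormal findings at Visit 1 will be used to reassess eligibility".
- The pregnancy test: "Obtain urine pregnancy test for women of childbearing potential. If positive, subject is ineligible to participate".
- The chest limit, stated within the garment-fitting step: "Subjects with an under bust chest circumference greater than 52 inches or less than 28 inches are not eligible to be enrolled".

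On enrollment, Protocol 9 says: "Subjects will be considered enrolled in the study when they have completed training, are successfully fitted with a WCD System", with the monitor connected and the system switched on. It continues: "Subjects who are consented but not enrolled per this definition will be classified as screen failures".

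On safety, Protocol 11 monitors adverse events "from the time the subject is considered enrolled through resolution". Both Protocol 11 and SAP 6.1 count an occurrence as an adverse event only if the investigator judges it at least possibly related to using the WCD system.

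At exit, Protocol 10 (Visit 2) asks for an ICD report that includes the parameters programmed at that time. Appendix A schedules ICD documentation at Visit 2 and at Early Withdrawal.

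**The concern.** The zone is a change to a therapeutic implant, and its only stated purpose is to serve the study's secondary endpoint. A change of that kind should be made only in people who will take part. It should have a defined end, and its own adverse consequences should be reportable.

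Read literally, the plan falls a little short on each count. Someone can be reprogrammed and then excluded the same day. No step asks anyone to decide whether the setting stays. An event caused by the ICD session, rather than by the WCD, has no place in the safety tables or in the Medical Monitor's review. The minimal-risk rationale in Protocol 7 (Device Regulatory Classification) rests on the WCD's disabled alarms and shocks and does not mention the ICD change, so it does not close the gap. What is at stake is subject protection and completeness of safety reporting, not the false-alarm result.

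**Working it through.** No formula or stated figure applies. The check sets the sections side by side.

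1. **Order of steps (Protocol 10, Visit 1).** Listed sequence: eligibility review, consent, demographics, ICD step with the zone request, medical history, Wearability Assessment, pregnancy test, training, baseline comfort scale, garment fitting with the chest limit. Checks after the request that can exclude a subject: wearability, pregnancy, chest size, so 3. No sentence holds the programming until they are passed.

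2. **Who is left uncovered (Protocol 9 and 10, Appendix A).** A subject who fails one of the three checks has consented but is not enrolled, and so is a screen failure. Visit 2 and Early Withdrawal procedures apply to enrolled subjects. No step in either document addresses the ICD settings of a screen failure who has already been reprogrammed.

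3. **Close-out for enrolled subjects (Protocol 10, Visit 2).** Visit 1 and exit reports both carry the programmed parameters, so a change can be traced by comparing them. What is absent is an instruction to decide whether to keep or revert the zone.

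4. **Adverse-event definition (Protocol 11, SAP 6.1).** The test is relation to the WCD system. Protocol 7 lists that system's components (WCD, charger, tablet, website, mobile device), and the subject's ICD is not among them. An event due solely to ICD interrogation or programming therefore fails the definition. Protocol 9 (Medical Monitor), the serious-event recording rule in Protocol 11 and the adverse-event row in Appendix A apply the same or a similar device-relatedness criterion, so they do not pick it up. Infection of the ICD system is on the anticipated list in Protocol 11, but only as an effect of using the study device.

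5. **Adverse-event window (Protocol 9, 10 and 11).** Interrogation must precede garment fitting. Successful fitting is one of the conditions for enrollment. The window opens at enrollment. Hence:

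   interrogation < fitting ≤ enrollment = start of window

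   This follows from the definitions and does not depend on bullet order. An active ICD is an inclusion criterion and Protocol 8 plans 130 to 135 subjects, so the Visit 1 interrogations before the window number 130 × 1 = 130 to 135 × 1 = 135, or 100% of enrolled subjects. Any later effect of the zone would fall inside the window in time but would still fail the relatedness test in step 4.

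6. **What cannot be computed.** The documents do not say how many ICDs already detect at 150 bpm, how many physicians would approve the zone, how many subjects would screen-fail after the ICD step, or how often ICD work causes an event. None of these is estimated here.

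**The case against.** The strongest defence is that the plan already limits the risk. Candidates are pre-screened, and eligibility, including skin condition, pregnancy and chest size, is reviewed at the start of Visit 1. The three later checks are therefore largely confirmatory. The list does not say that its order is binding; where sequence matters, as with interrogation before fitting, the text says so. A site could test and measure first and comply fully. The zone is a request that needs the physician's approval, no therapy change is requested, and qualified personnel do the interrogation. The WCD-only adverse-event definition matches the stated secondary endpoint. All of this stands, and it is why the point is minor. It does not remove the fact that a site following the list as written can reprogram a subject who is then excluded.

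Three stronger readings are tempting, and the documents do not support them:

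- A reader might infer that nothing records whether the zone is still in place. The exit ICD report does show it; only the direction to decide is missing.
- A reader might infer that subjects are never asked about ICD-related complaints. The weekly and exit questions cover any discomfort or injury, so a complaint can reach the site. The relatedness criterion is applied afterwards, when the investigator decides whether to record an adverse event.
- A reader might infer that the zone is dangerous. Neither document identifies a harm from it.

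The CRF and training manual are not part of these documents and may contain a relevant field. Statements of absence here cover the protocol and SAP only.

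**Conclusion.** The point holds as a minor patient-safety improvement. Two parts are firm: three excluding checks are listed after the programming request with no cover for a reprogrammed screen failure, and events due only to the ICD work are excluded from adverse-event recording both by definition and, for the Visit 1 interrogation, by timing. The missing keep-or-revert direction is a lesser matter that the subject's own physician would ordinarily handle.

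The interrogation count of 130 to 135 measures how often the timing gap occurs, not how often anyone is harmed. The number of subjects affected and any harm are unknown; with physician approval and a monitoring-only request, the risk is probably low. The primary endpoint, its analysis and the sample size are unaffected. The conclusion assumes that sites work through Visit 1 in the listed order and that no unseen site document already holds back the programming or captures these events.

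**What to change.** (a) In Protocol 10, Visit 1, place the Wearability Assessment, pregnancy test and chest measurement before the ICD programming request. Keep all ICD work before garment fitting. This means taking the chest measurement ahead of the fitting step in which the limit now sits.

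(b) In Protocol 11 and SAP 6.1, from the Visit 1 ICD interrogation onward, record events at least possibly related to ICD interrogation or to study-requested programming. Put them in a separate listing reviewed by the Medical Monitor. The WCD-related adverse-event endpoint keeps its present definition and window.

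Optional: for subjects whose ICD was changed, note the physician's keep-or-revert decision at Visit 2, Early Withdrawal or screen failure.

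The cost is a moved step, one extra listing with a short SAP revision, and a slightly wider scope for the Medical Monitor. If the optional item is adopted, add a CRF line, contact with the physician of each changed subject and, for some, a direct ICD session at the scheduled Visit 2 instead of a remote report.

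### The weekly adverse-event question looks back one week, but the call windows allow up to 11 days between calls, so short-lived events may go unasked

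*Protocol*

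**What the plan says.** Protocol Section 10, Weekly Phone Calls to Study Subject, sets the timing: "On each of Day 7 +/- 2, Day 14 +/- 2, Day 21 +/- 2, and Day 28 +/- 2 the site RC will call" the subject. For adverse events the instruction is to "Ask the subject if they have experienced any discomfort or injury during the previous week". In the same list, the coordinator records reasons for low usage "since the previous call".

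Under Visit 2 in the same section, the adverse-event question is "Ask the subject if they have experienced any discomfort or injury since the last phone call". Under Visit 1, subjects are told that the calls will cover usage "and if they experienced any discomfort or injury", with no look-back period.

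Protocol Section 11, Evaluation of Adverse Events, states the general rule. Adverse events "will be monitored continuously during the study", starting at enrollment. Subjects are to report all of them, and staff are to ask about new ones at every weekly call. No look-back limit is given there. The Wearability Assessment in Section 11 is repeated at Visit 2, and new or worsened findings that the investigator considers at least possibly related to the device are recorded as adverse events.

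**The concern.** Among the recurring questions, only the weekly adverse-event question has a fixed look-back, and that look-back does not match its own call windows. The usage question and the Visit 2 question both start at the last call and so cannot leave a gap. The weekly question can, and Visit 2 does not reach back to fill it by questioning. This makes the operative instruction in Section 10 narrower than the rule in Section 11.

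Device-related adverse events are a secondary endpoint (Protocol Section 8; SAP 4.3). The earlier studies in Protocol Section 6 reported mainly minor skin irritation, and all 8 events in the 30-day pilot (6 of 32 subjects) were minor. Minor events may resolve, or go unmentioned, unless someone asks. Any loss runs one way, towards a lower reported incidence.

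**Working it through.** The plan states no interval between calls, so there is no figure of its own to reproduce. The check is calendar arithmetic.

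**Inputs**
- Call windows (Protocol Section 10): Days 5–9, 12–16, 19–23 and 26–30.
- First contact: Visit 1, Day 0.
- Look-back of the weekly question, read literally: 7 days.
- Visit 2 (Appendix A): Day 30 to Day 35.

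**Formula.** Unasked days in an interval = max(0, gap − 7).

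**Extremes**
- Nominal days: every gap is 7, so 0 days are unasked.
- Longest gap between calls: 16 − 5 = 11 days. Unasked: 11 − 7 = 4. The Day 16 question reaches back to Day 9, so Days 5 to 9 are not covered.
- Longest wait for the first call: 9 − 0 = 9 days. Unasked: 9 − 7 = 2.
- Worst compliant schedule: Days 5, 16, 19, 30. The gaps are 5, 11, 3 and 11, so unasked days are 0 + 4 + 0 + 4 = 8.
- Last call to Visit 2: between 30 − 30 = 0 and 35 − 26 = 9 days. All are covered, because that question starts at the last call.

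**Averages under assumed call patterns.** The documents give no distribution of call days. Both patterns below take offsets evenly spread over −2, −1, 0, 1, 2.
- Same offset every week for a given subject: later gaps are all 7 days, so only the first call contributes. (0 + 0 + 0 + 1 + 2)/5 = 0.6 days, and 0.6/28 = 2.1%.
- Independent offsets: the difference k between two consecutive offsets has probability (5 − |k|)/25. The mean unasked time per later interval is (1×4 + 2×3 + 3×2 + 4×1)/25 = 20/25 = 0.8 days. The total is 0.6 + 3×0.8 = 3.0 days, and 3.0/28 = 10.7%. Of the 5⁴ = 625 whole-day schedules, 610 (97.6%) have at least one unasked day.

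**With the look-back running from the previous contact:** 0 unasked days in all 625 schedules.

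**The case against.** The strongest reply is that Section 11 already covers the point. It requires staff to ask about new events at every call without a time limit, and it tells subjects to report everything. In a section about weekly calls, the previous week is easily read as the time since the last call. The call CRF is not among the documents, so the wording used in practice is unknown. This stands as far as it goes: a coordinator following Section 11 would leave no gap. It does not remove the mismatch, because Section 10 is the detailed instruction for the call and gives the narrower period.

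A reader might infer that some wear days are never asked about and that events are under-collected. The documents do not support that. A gap needs both off-schedule calls and a strict seven-day reading. An event is then lost only if it starts and resolves within the gap and is not volunteered. An event still present when the look-back begins falls within the question, and persisting skin or musculoskeletal findings would be seen at Visit 2. No document gives evidence of lost events.

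A reader might also infer that early skin irritation is especially exposed, since earlier studies reported it after two or five days of wear. That fails on the arithmetic. A first call between Day 5 and Day 9 with a seven-day look-back starts no later than Day 2 and ends no earlier than Day 5, so Days 2 to 5 are covered in every permitted schedule.

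The 3.0-day average should not be read as the expected loss. All calls are scheduled with the subject at Visit 1, so a regular weekday is at least as plausible as independent offsets. A missed call would leave a longer gap, but that is non-adherence to the schedule, not a consequence of the windows.

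**Conclusion.** The point holds as a wording mismatch with a small, one-directional risk. Read literally, the weekly question may leave up to 4 days unasked between calls and up to 2 before the first call, and the worst compliant schedule leaves 8 in total. The average depends on call patterns that the documents do not give: zero on nominal days, about 0.6 of 28 days with a constant weekly offset, and about 3.0 of 28 with independent uniform offsets. These are unasked days, not lost events; the number of lost events cannot be derived from the documents.

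The consequence is confined to the adverse-event summaries, which are descriptive with no formal testing (SAP 4.5). The primary endpoint, power and significance level are unaffected. This is a low-priority improvement, worth making because it costs almost nothing.

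**What to change.** In Protocol Section 10, Weekly Phone Calls to Study Subject, replace the one-week look-back in the adverse-event question with: *since the previous completed call (since Visit 1 for the first call)*. Use the same wording on the call CRF, and record there the date of the last completed contact. This matches the usage question and the Visit 2 question, carries out the rule in Section 11, and also covers a missed call.

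The cost is one phrase in the protocol and the CRF, plus one date field. No extra contacts or staff are needed. The reported event count may rise slightly.
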